PSA (Procedural Sedation and Analgesia) refers to the suppression of a patient's consciousness to maintain vital heart and lung functions while using sedative and dissociative agents combined with analgesics during a medical procedure, with the goal of preventing or minimizing the patient's awareness, response, and memory of the event. However, the use of sedoanalgesic drugs carries significant risks, such as respiratory depression or hypotension, and requires that every patient be monitored and observed at least until they return to a presedation level of alertness. The need for the patient to stay in the emergency department for at least two hours and the requirement for staff to monitor the patient during this time present certain disadvantages, particularly in busy emergency departments. These concerns have led to the exploration of alternative approaches. Ultrasound (US)-guided peripheral nerve blocks are alternatives used in pain management during the reduction of forearm fractures. These techniques are widely used in outpatient settings, orthopedic surgeries, and postoperative pain management in operating rooms. Peripheral nerve blocks involve the use of local anesthetics and are defined as the infiltration of peripheral nerves with local anesthetic agents to reduce motor output and sensory input. Nerve blocks are effective in pain control, act quickly, have low complication rates, and do not require prolonged observation. As a result, the use of peripheral nerve blocks in pain management is increasing in emergency departments.

Patients presenting with forearm fractures to the emergency department will be included in the study. The need for reduction at the time of presentation will be determined by orthopedic doctors. Patients who require reduction and have an ASA classification of ASA 1-2 (ASA: American Society of Anesthesiologists, Table-1) will be included in the study and followed up. The patients will be randomly divided into two groups: Group P, where reduction will be performed under Procedural Sedation and Analgesia (PSA), and Group B, where reduction will be performed under ultrasound-guided infraclavicular nerve block (ICB). Randomization will be done by assigning the first 5 patients to Group P and the next 5 patients to Group B (the procedures are described in detail below), and the following parameters will be evaluated:

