Allergy to drugs used for sedation analgesia and peripheral nerve block Hemodynamically unstable Patients with ASA 3-4 classification (for those in the PSA group) Coagulopathy, liver or kidney failure Patients with opioid, alcohol, or substance abuse Skin infection or open wound at the site where local anesthetic will be applied Pregnant or suspected of being pregnant Those who do not give written and verbal consent

Sample Size: For the planned analyses in this study, the sample size calculation was based on the study by Tekin et al. titled 'Can ultrasound-guided infraclavicular block be an alternative option for forearm reduction in the emergency department? A prospective randomized study.' In that study, a 30% difference between the two groups was found to be significant, and thus, this article was used as a reference for our study. Based on this reference article, with an effect size of 0.5 (medium), an α level of 0.05, and a power of 0.80, it was determined that a total of 78 participants (39 in each group) would be sufficient. The sample size analysis was conducted using the GPower 3.1 program.

Volunteer recruitment for the study will be terminated once the total of 78 patients, as determined by the power analysis, is reached.

The study received approval from the Ankara Etlik City Hospital Ethics Committee on April 24, 2024 (approval code: AEŞH-EK1-2024-0040). However, patient recruitment has not yet started.

Volunteer Recruitment Start: September 1, 2024 [Expected] Primary Completion: June 1, 2025 [Expected] Study Completion: December 1, 2025 [Expected]

2. Statistical analysis

Statistical analysis will be performed using the SPSS 23.0 statistical software package. In the descriptive findings section, categorical variables will be presented as numbers and percentages, while continuous variables will be presented as mean \pm standard deviation for normally distributed data and as median (minimum, maximum) for non-normally distributed data. The normality of the distribution of continuous variables will be assessed using the Kolmogorov-Smirnov test. Comparisons between groups for categorical variables will be evaluated using the chi-square test. For normally distributed quantitative variables, comparisons between the three groups will be made using the ANOVA test. For non-normally distributed quantitative variables, the Kruskal-Wallis test will be used. A p-value of < 0.05 will be considered statistically significant in this study

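### The stated effect size of 0.5, alpha 0.05 and power 0.80 call for 128 patients, not 78; with 39 per group the power at 0.5 is about 59%

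*Combined protocol and SAP*

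**What the plan says.** The Sample Size paragraph (section 1, Protocol) takes an earlier randomised study of the same block as its reference and reports that there "a 30% difference between the two groups was found to be significant". It then says that, "with an effect size of 0.5 (medium), an α level of 0.05, and a power of 0.80", "a total of 78 participants (39 in each group) would be sufficient". For the method it says only: "The sample size analysis was conducted using the GPower 3.1 program". The next paragraph ends recruitment at 78 and gives no allowance for dropout.

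The design has two arms: "The patients will be randomly divided into two groups". Section 2, Statistical analysis, plans chi-square tests for categorical variables and ANOVA or Kruskal-Wallis for quantitative ones, with this threshold: "A p-value of < 0.05 will be considered statistically significant in this study".

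The plan does not state the endpoint behind the calculation, the effect-size metric, the test, the sidedness, or the rates or standard deviation from which 0.5 was derived.

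**The concern.** On Cohen's scale for a standardised mean difference, 0.5 is the benchmark for a medium effect, and at 80% power it is well known to need about 64 patients per group. A claim of 39 per group is too small by roughly two fifths.

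This is the plan's only justification of its size. If 0.5 is meant as a standardised difference in the pain score (NRS), the trial would miss a true difference of that size about 41% of the time (1 − 0.587), where the plan implies 20%. A non-significant result could then be taken to show that sedation and block relieve pain equally well. Because recruitment stops at exactly 78, nothing later in the plan corrects the shortfall.

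**Working it through.** **Inputs from the Sample Size paragraph.** Effect size 0.5, labelled medium; alpha 0.05; power 0.80; 39 per group, 1:1. Sidedness is not stated; two-sided is assumed and one-sided is also shown.

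**Step 1. Try to reproduce 78 from the stated inputs.** The normal approximation for two means is

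n per group = 2(z₀.₉₇₅ + z₀.₈₀)² / d² = 2 × 7.849 / 0.25 = 62.8, so 63.

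The exact noncentral t calculation gives 63.77, so 64 per group and **128 in total**. One-sided it gives 50.15, so 51 per group and 102 in total. The stated 78 is not reproduced.

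**Step 2. Power with 39 per group at d = 0.5.** The noncentrality is 0.5 × √(39/2) = 2.208, with 76 degrees of freedom and a two-sided critical value of 1.992. Power is **58.7%**. The normal approximation gives 59.8%. One-sided, power is 70.7%. For a Mann-Whitney test with normally distributed data (relative efficiency 0.955) it is about 57%.

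**Step 3. Difference detectable with 80% power at 39 per group.** d = **0.64** two-sided, 0.57 one-sided.

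**Step 4. Other readings of 0.5** (two-sided unless noted, 80% power):

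| Reading | Total N |
|---|---|
| Mann-Whitney, normal data | 134 |
| Mann-Whitney, least favourable efficiency (0.864) | 148 |
| Cohen's h = 0.5 | 126 |
| ANOVA f = 0.25 (the f that equals d = 0.5), two groups | 128 |
| ANOVA f = 0.5, two groups | 34 |
| ANOVA f = 0.5, three groups | 42 |
| Chi-square w = 0.5, 1 df | 32 |
| Chi-square w = 0.5, 2 df | 39 |
| Paired t, d = 0.5 | 34 |

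None gives 78. The 2 df chi-square result is 39 in total. It becomes 78 only if that total is misread as a per-group figure. In addition, 0.5 is not the medium benchmark for f or w.

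**Step 5. Try the 30% difference instead.** For two proportions (pooled variance under the null, no continuity correction),

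n per group = [z₀.₉₇₅√(2p̄(1−p̄)) + z₀.₈₀√(p₁(1−p₁) + p₂(1−p₂))]² / (p₁−p₂)².

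With 50% against 80%, p̄ = 0.65: (1.322 + 0.539)² / 0.09 = 38.48, so **39 per group, 78 in total**. The same holds for 20% against 50%. The number therefore reproduces, but only from rates the plan does not give. Over all pairs 30 points apart, in steps of 5 points, the requirement runs from 22 to 43 per group, so a 30-point gap alone does not fix the size.

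**Step 6. Can 30 points and 0.5 describe the same binary effect?** For a 30-point gap, Cohen's h is smallest at 35% against 65%, where it is 0.61. For 50% against 80% it is 0.64. With equal groups, w = 0.30 / (2√(p̄(1−p̄))), which is largest at 0% against 30%: 0.30 / (2√(0.15 × 0.85)) = 0.42. Neither measure can equal 0.5.

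**The case against.** The strongest reply is that the plan never says 0.5 is a standardised mean difference, so 128 and 59% are conditional on a reading it does not state. The exact match with 50% against 80% suggests that the calculation was done on proportions. On that view 78 is right for its inputs and the slip is in the description. The plan does use chi-square tests and lists binary outcomes such as reduction success and need for rescue treatment. Nor does the paragraph say that the calculation concerns the NRS.

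Much of this stands. The documents cannot show whether the total or the effect size is the wrong entry, and the consequence for the NRS applies only if the NRS was the endpoint. But the printed statement is wrong either way, because 50% against 80% corresponds to h = 0.64, not 0.5.

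A second reply is that a more efficient analysis could reach 80% power with 78. Averaging three NRS measurements with a correlation of 0.4 between them gives a total of 78 at f = 0.25 (86 at a correlation of 0.5). Adjusting for baseline with a correlation of about 0.63 gives roughly 80% power at 39 per group. Both correlations are assumptions, and the plan specifies neither analysis. Section 2 plans unadjusted between-group comparisons, and for two groups ANOVA is the same test as the two-sided t-test in Step 1.

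**Conclusion.** The concern holds. As written, the inputs do not give 78. Read as a standardised mean difference with a two-sided test, they need 128 patients, and 39 per group gives 58.7% power against the 80% claimed. The difference detectable with 80% power is 0.64. Relaxing to a one-sided test does not close the gap (102 patients, 70.7% power).

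The figures 128 and 58.7% assume Cohen's d, a two-sided 5% test and no baseline adjustment. The finding that 0.5 does not lead to 78 is broader: it holds for every reading in the Step 4 table. All power figures assume complete data. With a 10% loss, taken as an illustration (about 35 per group), power at d = 0.5 falls to about 54%.

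**What to change.** The sponsor should first recover the program record and state the endpoint, test, sidedness and inputs that produced 78. Then, keeping 78, make one of two corrections.

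- **If the calculation was for the NRS as primary endpoint:** state that 39 per group with a two-sided 5% test gives 80% power for a standardised difference of 0.64, and 59% power for 0.5.
- **If it was for proportions:** remove the effect size of 0.5 and its medium label, name the binary endpoint as primary, and give the two proportions used with their source. The pair 50% and 80% reproduces 39 per group, but the sponsor must confirm that these were the values.

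The cost is wording only, with no extra patients. The stated power or detectable effect becomes less favourable. The protocol says that recruitment had not begun when it was written; if that is still so, the correction can be made before any data exist.

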Pain levels at the time of arrival, post-procedure but before reduction, and after reduction will be recorded using the Numeric Rating Scale (NRS). (NRS ranges from 0-10, with 0 representing no pain and 10 representing unbearable pain.)

The success of the reduction procedure will be assessed, noting whether additional reduction procedures were required, and the findings on control X-rays after each reduction (radial height, radial inclination, and volar tilt) will be recorded and evaluated by orthopedic doctors. The length of stay in the emergency department will be recorded as the time from the patient's arrival to discharge.

Side effects/complications during the procedures will be recorded.

The need for rescue treatment during the procedure will be evaluated. If the NRS is above 5, the first-line rescue analgesic treatment will be 50 or 100 mg of tramadol IV, administered in 100 cc of normal saline over 15 minutes. If the pain remains above NRS 5, the second-line

treatment will be 50 mcg of fentanyl IV, administered in 100 cc of normal saline over 15 minutes.

The need for pain medication within 24 hours after discharge will be assessed by calling the patients.

Patient satisfaction will be recorded using a 5-point Likert scale (1: very poor, 2: poor, 3: fair, 4: good, 5: very good).

The same satisfaction survey will be administered to the orthopedic doctors who performed the reduction.

Procedures for the groups will be as follows before reduction: The PSA protocol for Group P will be performed by experienced emergency physicians who are skilled in sedation analgesia, advanced life support, and advanced airway management. The patient will be monitored by an experienced doctor or nurse during the sedation period until recovery. Emergency equipment will be readily available in case of any complications. The PSA protocol will include IV ketamine administered at a dose of 1-2 mg/kg. If the NRS remains above 5, additional doses of 0.25-1 mg/kg may be repeated every 5 to 10 minutes as needed. The decision to discharge the patient will be based on the modified Aldrete score, one of the recovery scoring systems.

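### Arrival NRS is recorded for every patient but has no stated role when later NRS is compared, and the SAP's three groups should read two

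*Combined protocol and SAP*

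**What the plan says.** The design in section 1 (Protocol) has two arms: "The patients will be randomly divided into two groups", sedoanalgesia (Group P) and infraclavicular block (Group B). The Sample Size paragraph agrees: "a total of 78 participants (39 in each group) would be sufficient". No third arm is described anywhere.

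On pain, section 1 states: "Pain levels at the time of arrival, post-procedure but before reduction, and after reduction will be recorded". Every patient therefore has a baseline NRS and two later values.

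Section 2 (Statistical analysis) sets tests by variable type only. Categorical variables get chi-square. For normally distributed quantitative variables, "comparisons between the three groups will be made using the ANOVA test". For the rest, "For non-normally distributed quantitative variables, the Kruskal-Wallis test will be used". The section does not name NRS or any primary time point. It mentions no covariate, change score or repeated-measures model, and no estimated difference with a confidence interval.

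**The concern.** There are two separate points.

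1. **Number of groups.** The SAP's three groups contradict the two-arm design. A reader cannot tell whether this is a slip, a leftover from another plan, or a reference to the three NRS times.
2. **Use of the baseline.** Pain during reduction is part of the main aim, and arrival pain is an obvious candidate to predict later pain. As written, the later scores would be compared with no allowance for it. At stake are the precision of the NRS comparison and its exposure to a baseline difference between two small groups. Allocation is also predictable ("Randomization will be done by assigning the first 5 patients to Group P and the next 5 patients to Group B"), so arrival pain could differ by more than chance. With no rule set in advance, the analyst could also choose among raw, change and adjusted scores after seeing the data.

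**Working it through.** **Inputs from the documents.** 39 per group, α = 0.05, effect size 0.5 and target power 0.80 (Sample Size paragraph); NRS at three times (section 1).

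**Assumptions.** The correlation r between arrival and later NRS is not given; 0.2, 0.3, 0.5 and 0.6 are used. The NRS SD is not given, so results are in SD units. Tests are taken as two-sided, which the plan does not state.

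**Step 1: the plan's own figure.** The plan states "with an effect size of 0.5 (medium), an α level of 0.05, and a power of 0.80". If 0.5 is Cohen's d, a two-sided t-test needs 64 per group (128 in total), not 39. At 39 per group its power is 58.7%. A 30-point difference in proportions of 50% vs 20%, or 80% vs 50%, does give 39 per group (power 80.5%), but those rates are not in the documents. The 78 is therefore not reproduced from d = 0.5. The power figures in step 4 apply only if 0.5 is d on the NRS.

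**Step 2: two versus three groups.** On two simulated groups of 39, ANOVA and the equal-variance t-test both gave p = 0.1132. Kruskal-Wallis and the asymptotic Mann-Whitney test without continuity correction both gave p = 0.1578. Correcting the count changes nothing numerically.

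**Step 3: precision.** ANCOVA multiplies the outcome variance by 1 − r². The 95% CI half-width for the group difference is

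t(0.975, df) × √(2(1 − r²)/39), with df = 76 unadjusted and 75 adjusted.

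- Unadjusted: 1.992 × √(2/39) = 1.992 × 0.2265 = 0.451 SD.
- r = 0.5: 1.992 × √(1.5/39) = 1.992 × 0.1961 = 0.391 SD.

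**Step 4: power, if d = 0.5.** The noncentrality is 0.5/√(1 − r²) × √(39/2), so 2.208 unadjusted and 2.208/0.866 = 2.550 at r = 0.5.

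| r | Variance factor 1 − r² | Half-width (SD) | Narrower by | Power if d = 0.5 |
|---|---|---|---|---|
| unadjusted | 1 | 0.451 | – | 58.7% |
| 0.2 | 0.96 | 0.442 | 2% | 60.4% |
| 0.3 | 0.91 | 0.430 | 5% | 62.7% |
| 0.5 | 0.75 | 0.391 | 13% | 71.1% |
| 0.6 | 0.64 | 0.361 | 20% | 77.8% |

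ANCOVA with 39 per group detects 0.643 residual SD at 80% power. Reaching 80% at d = 0.5 therefore needs r = √(1 − (0.5/0.643)²), about 0.63. A simulation of the ANCOVA (5000 runs) gave 60.4%, 63.3%, 69.8% and 77.7% at the four values of r.

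**Step 5: cost if r = 0.** Average chance imbalance in the covariate multiplies the variance by 1 + 1/74. At r = 0, power goes from 58.7% to 58.1%. The same factor widens each adjusted half-width by √(75/74) − 1, about 0.7% (for example 0.442 to 0.445 SD at r = 0.2).

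**Step 6: baseline imbalance.** By chance alone, the difference in mean arrival NRS has SE √(2/39) = 0.226 SD, a 95% range of about ±0.44 SD. Left unadjusted, an imbalance of 0.44 SD moves the later difference by r × 0.44: 0.13 SD at r = 0.3 and 0.22 SD at r = 0.5.

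**Step 7: change score.** Its variance factor is 2(1 − r), for example 1.4 at r = 0.3. It is worse than no adjustment whenever r is below 0.5.

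**The case against.** The strongest reply is that the second point concerns efficiency only. The unadjusted test is valid, and no bias or inflated error rate is shown. The group-count error is only wording. The SAP gives no variable a specific role, so an adjusted analysis is not excluded; it is just not pre-specified. All of this is correct.

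The gain also rests on an unknown r that could well be low. Both groups receive analgesia before reduction, and further treatment is triggered above NRS 5, which pushes later scores toward the floor. One simulation used an integer 0–10 score, arrival mean 7.5 and SD 1.5, later latent SD 2 with reference-group latent mean 0 to 1, and a shift of 0.5 SD (all assumed). A latent correlation of 0.5 fell to an observed 0.37–0.42, with an interval 6–9% narrower; a latent 0.3 gave 2–3%. The 13–20% gains need an observed r of 0.5–0.6, which nothing in the documents supports. This stands as a limit on the size of the benefit.

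A further objection is that a mean-based model suits a bounded, skewed score poorly. This carries less weight: in simulation of a bounded integer score with a heavy floor, ANCOVA kept type I error at about 5%, with standard errors 2–11% smaller. The Mann-Whitney sensitivity analysis is unadjusted and addresses a different quantity, so it supplements the ANCOVA and does not check its assumptions.

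Finally, if the three groups meant the three NRS times, one-way ANOVA and Kruskal-Wallis would be wrong, because those measurements are within patient. The text says groups, so this reading is unlikely, but the correction should rule it out.

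**Conclusion.** Both points hold. The group count must be corrected for consistency, with no numerical effect on the two-arm reading. Giving arrival NRS a pre-specified role is a worthwhile improvement to a valid analysis and should be made.

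Its size depends on r: from about 2% narrower intervals at r = 0.2 to 20% at r = 0.6, whatever the true effect. The risk is under one percentage point of power if r is zero. The rise in power from 59% toward 78% applies only if 0.5 is Cohen's d on the NRS, tested two-sided. If the trial was sized on a proportion, the power figures do not describe the outcome it was sized for, though the NRS half-widths still hold.

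Adjustment removes only the part of a baseline imbalance that arrival pain carries. It does not repair the predictable allocation in runs of five, and it does not resolve the unreproduced sample size. Confidence is medium, because r is unknown.

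**What to change.** Replace the ANOVA and Kruskal-Wallis sentences in section 2 with:

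> NRS after reduction (and, separately, NRS after the procedure but before reduction) is compared between Group P and Group B by ANCOVA with arrival NRS as covariate, reporting the adjusted mean difference and 95% CI, with Mann-Whitney as a sensitivity analysis. Other quantitative outcomes are compared between the two groups by t-test if normally distributed and Mann-Whitney otherwise.

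The sponsor should also state which of the two later NRS times is primary, so that the other is clearly secondary.

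The cost is SAP wording and one degree of freedom. Arrival NRS is already recorded, so no data, visits or patients are added. The document states that recruitment had not begun, so on its own account the change can still be made before any outcome is seen.

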Evaluation of the Efficacy of Procedural Sedoanalgesia and Infraclavicular Nerve Blockade on Analgesia in Forearm Fractures in the Emergency Department

1. Protocol

Trauma patients constitute a significant portion of emergency department visits. Forearm fractures are common upper extremity fractures in adult patients. A forearm fracture can present as an isolated radius fracture, an isolated ulna fracture, or a double bone radius-ulna fracture. Forearm fractures cause severe pain, both due to the fracture itself and during the reduction process. Pain management is crucial in emergency departments (ED). Therefore, multimodal approaches are available to reduce or eliminate pain during the reduction process. Procedural sedation and analgesia (PSA), which is widely used in emergency departments and effectively reduces pain, is particularly common. However, recent literature suggests the use of peripheral regional block techniques over the use of multiple nonsteroidal anti-inflammatory and/or opioid analgesics for pain palliation.

The aim of our study is to evaluate the success of reduction and pain palliation during the reduction process in patients with forearm fractures using PSA and ultrasound-guided infraclavicular nerve block (ICB). The secondary aim is to compare patient comfort, physician comfort, side effects, length of stay in the emergency department, and the need for pain medication after discharge between these two procedures, and to determine the most appropriate method. With this study, we aim to contribute to practical applications for achieving optimal pain control in patients with forearm fractures in emergency department settings.

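### One unadjusted p < 0.05 rule covers every comparison, with no testing order, no exploratory label and no rule for success on a two-part main aim

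*Combined protocol and SAP*

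**What the plan says.** Section 2 (Statistical analysis) ends with a single rule: "A p-value of < 0.05 will be considered statistically significant in this study". The section assigns tests by type of variable. It lists no individual comparisons, sets no order among them, makes no adjustment, and labels nothing exploratory.

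The outcomes are in section 1 (Protocol). The main aim is to "evaluate the success of reduction and pain palliation during the reduction process", which is two outcomes. Under the secondary aim, the trial will "compare patient comfort, physician comfort, side effects, length of stay in the emergency department, and the need for pain medication after discharge"; the same sentence adds that the study should establish which of the two techniques is preferable.

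The list of recorded parameters in section 1 goes further. On pain: "Pain levels at the time of arrival, post-procedure but before reduction, and after reduction will be recorded". It also records any need for further reduction, three radiographic measurements, rescue analgesia, and satisfaction of patient and orthopaedic doctor.

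The Sample Size paragraph works "with an effect size of 0.5 (medium), an α level of 0.05, and a power of 0.80" and concludes that "a total of 78 participants (39 in each group) would be sufficient". It does not say which outcome this refers to.

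**The concern.** A threshold of 0.05 limits the false-positive risk of one test. The conclusion this study wants, a preferred technique, draws on many tests. The plan does not say which of them carry that conclusion or how they combine. Without such a rule, a chance result on any one outcome can be declared significant on the same footing as the main aim, and a reader of the report could not tell which findings were confirmatory.

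The main aim has the same gap on a smaller scale. It contains two outcomes, and the plan does not say whether a technique must do better on both or on only one. The answer decides whether testing each at 0.05 is acceptable.

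**Working it through.** **The plan's own figure.** The plan gives a per-test level of 0.05 and no study-wide error rate, so there is no family-wise figure to reproduce. What can be computed is the family-wise rate that the rule implies.

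**Step 1: count the comparisons.** The count is inferred from section 1. NRS at arrival is a baseline value and is left out.

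| Outcome | Separate tests | X-ray and repeat-reduction items folded into one success outcome |
|---|---|---|
| NRS before reduction; NRS after reduction | 2 | 2 |
| Reduction success | 1 | 1 |
| Additional reduction | 1 | – |
| Radial height, radial inclination, volar tilt | 3 | – |
| Rescue treatment | 1 | 1 |
| Side effects | 1 | 1 |
| Length of stay | 1 | 1 |
| Analgesic need in the 24 h after discharge | 1 | 1 |
| Patient satisfaction; doctor satisfaction | 2 | 2 |
| **Total** | **13** | **9** |

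**Step 2: chance of at least one p < 0.05 when no true difference exists on any outcome.** For m independent tests it is 1 − 0.95^m:

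- m = 13: 1 − 0.95^13 = 0.487
- m = 9: 1 − 0.95^9 = 0.370
- m = 2: 1 − 0.95^2 = 0.0975

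For tests with a common correlation ρ, write c = 1.96, Φ for the standard normal distribution function and φ for its density. The chance is 1 − ∫ [Φ((c − √ρ·x)/√(1−ρ)) − Φ((−c − √ρ·x)/√(1−ρ))]^m φ(x) dx, evaluated numerically. The documents give no correlations, so ρ is an assumption and is shown as a range.

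| Comparisons | ρ = 0 | ρ = 0.3 | ρ = 0.5 | ρ = 0.8 |
|---|---|---|---|---|
| 13 | 48.7% | 41.8% | 33.4% | 19.2% |
| 9 | 37.0% | 32.6% | 26.9% | 16.5% |
| 2 (main aim, either suffices) | 9.8% | 9.5% | 9.1% | 7.8% |

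**Step 3: the main aim if both outcomes are required.** A false claim then needs p < 0.05 on every outcome, including any outcome with no true difference. That probability is at most 0.05, so no adjustment is needed.

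**Step 4: power cost of Holm.** Inputs are 39 per group from the Sample Size paragraph and a two-sided two-sample t-test (assumed, since the plan does not state the sidedness). The standardised difference detectable with 80% power at 0.05 is 0.643. At 0.025 the power for that difference is 70.9%.

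The value 0.643 is used because the plan's inputs do not reproduce its sample size for this test: an effect size of 0.5 needs 64 per group. With 39 per group and 0.5, power is 59% at 0.05 and 47% at 0.025. This mismatch does not affect Step 2, which depends only on the test level, the number of tests and their correlation.

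**The case against.** The strongest reply is that the main aim joins its two outcomes with an *and*. If both must be shown, each may be tested at 0.05 and the main aim has no inflation. This stands. A reader might infer that the main aim already carries a 9% to 10% error rate, but the documents do not support that as a fact: they do not say that either outcome alone is enough.

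A second reply is that secondary outcomes need no adjustment, and that naming one primary endpoint and treating the rest as secondary would settle the confirmatory question at 0.05. That is correct as a remedy, and Holm is only one option. It does not describe the plan as written, where no single primary endpoint is named, the one threshold covers the whole study, and the secondary-aim sentence itself contains the choice of technique.

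Third, the count is soft. Section 2 lists no tests, and the X-ray measures and repeat reduction stand in the same sentence as the success assessment. A firm statement of at least 13 tests, or of a 33% to 49% risk, goes further than the documents allow. Nor is 33% a floor. Outcomes may be strongly correlated, and some are linked by design, since an NRS above 5 triggers rescue.

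Fourth, a reader might infer that the plan promises a 5% study-wide error rate and breaks it, or that it will recommend whichever technique first crosses 0.05. It says neither. It gives a per-test threshold and no decision rule. The fault is that such a selection is left open.

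**Conclusion.** The concern holds in this form: the plan applies 0.05 to every comparison, without an order or an exploratory label, although its main aim has two parts and the results are to inform a choice of technique. With about 9 to 13 inferred comparisons and no true differences on any of them, the chance of at least one p < 0.05 is about 27% to 49% for common correlations of 0.5 down to 0, and about 17% to 19% at 0.8. The count and the correlations are assumptions, but no plausible combination brings the figure back to 5%.

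For the two main-aim outcomes the figure is about 8% to 10% if either suffices, taking one test for each outcome, and at most 5% if both are required. The missing success rule is therefore part of the finding. This should be corrected but does not prevent the trial from going ahead.

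**What to change.** Section 1 says that recruitment had not begun when the document was written. If that still holds, make these changes before the first patient is enrolled:

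1. Tie each main-aim outcome to one variable: one NRS time point for pain, and one definition of reduction success. Until this is done, no two-test procedure can be run, because each outcome could be represented by several tests.
2. State whether success needs both outcomes or either one.
3. If both are required, test each at two-sided 0.05. If either suffices, use Holm: the smaller p against 0.025 and, if that is met, the other against 0.05.
4. Replace the closing sentence of section 2. Suggested text: *The two main-aim outcomes are tested as specified above. All other comparisons are exploratory, are reported as estimates with 95% confidence intervals, and are not used alone to name the preferred method.*

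The cost is a few sentences, two clinical definitions to be agreed, and some power. Under Holm, power for the outcome tested first falls from 80% to about 71% at a standardised difference of 0.64 with 39 per group. If both outcomes are required, the power to succeed on both is lower than for either one: with 80% on each and independence (assumed), 0.80 × 0.80 = 64%.
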